5.6.4.4. Quizartinib Dose Reduction Rules and Definitions

The dose of quizartinib will be reduced stepwise from 60 mg/day to 30 mg/day or from 30 mg/day to 20 mg/day, based on the following criteria:

QTcF (QT interval corrected with Fridericia's formula) Prolongation

- Grade 2 (QTcF average of triplicate readings > 480 msec)
 - The dose will be reduced without interruption.
 - If 20 mg/day is the current dose, dosing will be interrupted for up to 14 days. If QTcF returns to within 30 msec of baseline or ≤ 450 msec within 14 days, treatment may be resumed at 20 mg/day.
- Grade 3 (QTcF average of triplicate readings > 500 msec)
 - Dosing will be interrupted for up to 14 days. If QTcF returns to within 30 msec of baseline or ≤ 450 msec within 14 days, treatment may be resumed at a reduced dose.
 - If 20 mg/day is the current dose, dosing will be interrupted for up to 14 days. If QTcF returns to within 30 msec of baseline or ≤ 450 msec within 14 days, treatment may be resumed at 20 mg/day. If Grade 3 event returns, treatment will be discontinued.
- Grade 4 (QTcF >500 msec or >60 msec change from baseline, and Torsade de pointes or polymorphic ventricular tachycardia or signs/symptoms of serious arrhythmia)
 - Treatment will be discontinued.

See Section 8.5 for clinical guidelines for the management of QT prolongation.

Non-hematologic Toxicity

Grade 3 or 4 related to quizartinib and persisting >48 hours without improvement to \leq Grade 2.

- Dosing will be interrupted for up to 14 days.

- If toxicity improves to \leq Grade 1 within 14 days, treatment may be resumed at the reduced dose.

Myelosuppression

In a subject with CRp or CRi, the dose may be reduced at the Investigator's discretion if:

- The subject has been treated for a minimum of 2 cycles.
- Platelet count is $<100 \times 10^9/L$ and ANC is $\leq 1000 \times 10^9/L$.
- Marrow blast count is $<5\%$.
- There is no evidence of extramedullary disease.

Initiation of concomitant treatment with a strong CYP3A4 inhibitor is identified in [Appendix 1: List of Potential QT Prolonging Drugs, CYP3A4 Inhibitors/Inducers, and P-glycoprotein Inhibitors/Inducers](#).

The dose will be reduced one level (60 mg to 30 mg or 30 mg to 20 mg) when treatment with a strong CYP3A4 inhibitor is initiated.

- A subject taking a strong CYP3A4 inhibitor at enrollment will initiate quizartinib administration at 20 mg/day. The dose will be escalated to 30 mg/day at day 16 if the QTcF interval is less or equal to 450 msec prior to or at the day 15 ECG evaluations.

Subjects receiving a reduced quizartinib dose may be re-escalated one level to 30 mg/day or to 60 mg/day except for reductions due to Grade 3 QTcF prolongation. If the dose was reduced for toxicity, all events responsible for dose reduction must have resolved to \leq Grade 1. If the dose was reduced for a strong CYP3A4 inhibitor, the prior dose of quizartinib may be resumed when the inhibitor is withdrawn.

5.6.4.5. Quizartinib Dose Interruption for HSCT

If a subject undergoes HSCT, quizartinib should be discontinued 7 days before the start of a conditioning regimen. For subjects randomized to the quizartinib arm who undergo HSCT, treatment with quizartinib may be resumed at 30 to 100 days after the transplant. A window of +7 days will be allowed after day 100. Quizartinib may be restarted if:

- Subject has an ANC $>1 \times 10^9/L$ and platelet count $>50 \times 10^9/L$ without platelet transfusion support within 1 week, or a platelet count $>25 \times 10^9/L$ without platelet transfusion support within 2 weeks prior to first dose.
- Subject does not have (1) active acute, or \geq Grade 3 graft versus host disease (GVHD) or (2) active GVHD therapy (not prophylaxis) initiation within 21 days.

The starting dose of quizartinib post-HSCT should be 30 mg daily unless the subject is receiving a strong CYP3A4 inhibitor, in which case the starting dose should be 20 mg daily. Subjects will dose escalate starting on Day 16 if the QTcF interval is less or equal to 450 msec prior to or at the day 15 ECG evaluations.

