In subjects receiving a reduced dose of quizartinib, the dose may be re-escalated stepwise from 20 mg to 30 mg to 60 mg, except following Grade 3 QTcF prolongation. If the dose was reduced due to toxicity, all events responsible for dose reduction must have resolved to ≤ Grade 1. If the dose was reduced due to administration of a strong CYP3A4 inhibitor, the prior dose can be resumed when the inhibitor is withdrawn.

If a subject undergoes HSCT, quizartinib should be discontinued 7 days before the start of a conditioning regimen. For a subject who was randomized to and received quizartinib, treatment with quizartinib may be resumed at 30 to 100 days after the transplant. Quizartinib may be restarted if:

- Subject has an ANC > $1 \times 10^9/L$ and platelet count > $50 \times 10^9/L$ without platelet transfusion support within 1 week, or a platelet count > $25 \times 10^9/L$ without platelet transfusion support within 2 weeks prior to first dose.
- Subject does not have (1) active acute, or ≥ Grade 3 graft versus host disease (GVHD) or (2) active GVHD therapy (not prophylaxis) initiation in the preceding 21 days.

Follow-up

After study treatment is discontinued, subjects will be followed for 30 days for safety. Assessment of best response to chemotherapy should be conducted at Day 29 (±14 days) or prior to starting subsequent AML therapy. Subjects will then enter long term follow-up every 3 months for collection of information on subsequent AML treatment, remission status, and survival, including the cause and date of death.

Salvage Chemotherapy

The Investigator will pre-select the specific salvage chemotherapy regimen before randomization of each subject. All salvage chemotherapy will be administered during 28-day cycles. The start of Cycle 2 (MEC, FLAG-IDA, or LoDAC) and subsequent cycles (LoDAC) may be delayed for up to 14 days to allow for recovery from toxicity. Dose reductions are allowed for toxicity but must be documented in the source record.

Low Dose Cytarabine (LoDAC)

Cytarabine (20 mg) will be administered twice daily by subcutaneous injection for 10 days (Days 1 through 10) over continuous 28-day cycles. A delay of up to 14 days between cycles is allowed for recovery from toxicity.

MEC Chemotherapy

- Mitoxantrone ($8 \text{ mg/m}^2/\text{day}$) will be administered by 5 minute intravenous (IV)

injection for 5 days (Days 1 through 5).

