8. Discontinuation of prior AML treatment before the start of study treatment (except hydroxyurea or other treatment to control leukocytosis) for at least 2 weeks for cytotoxic agents, or for at least 5 half-lives for non-cytotoxic agents.
9. Serum creatinine $\leq 1.5 \times$ upper limit of normal (ULN), or glomerular filtration rate > 25 mL/min, as calculated with the Cockcroft-Gault formula.
10. Serum potassium, magnesium, and calcium (serum calcium corrected for hypoalbuminemia) within institutional normal limits. Subjects with electrolytes outside the normal range will be eligible if these values are corrected upon retesting following any necessary supplementation.
11. Total serum bilirubin $\leq 1.5 \times$ ULN.
12. Serum aspartate transaminase (AST) and/or alanine transaminase (ALT) $\leq 2.5 \times$ ULN.

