5.4.2. Exclusion Criteria

Candidates will be excluded from study entry if any of the following criteria are met at screening or other specified time point:

1. Acute promyelocytic leukemia (AML subtype M3)
2. AML secondary to prior chemotherapy for other neoplasms, except AML secondary to prior MDS
3. History of another malignancy, unless the candidate has been disease-free for at least 5 years
 - Candidates with treated non-melanoma skin cancer, carcinoma in situ, or cervical intraepithelial neoplasia are eligible regardless of the time spent disease-free, if they have completed definitive treatment
 - Candidates with organ-confined prostate cancer, with no evidence of recurrent or progressive disease, are eligible if hormonal therapy has been begun, or if the tumor has been surgically removed or treated with definitive radiotherapy
4. Persistent, clinically significant $>$ Grade 1 non-hematologic toxicity from prior AML therapy
5. Clinically significant GVHD or GVHD requiring initiation of treatment or treatment escalation within 21 days, and/or $>$ Grade 1 persistent or clinically significant non-hematologic toxicity related to HSCT
6. History of or current, central nervous system involvement with AML
7. Clinically significant coagulation abnormality, such as disseminated intravascular coagulation
8. Prior treatment with quizartinib or participated in a prior quizartinib study

9. Prior treatment with a FLT3 targeted therapy including sorafenib or investigational FLT3 inhibitors (not including the multi-kinase inhibitor, midostaurin)
10. Major surgery within 4 weeks prior to screening
11. Radiation therapy within 4 weeks prior to screening
12. Uncontrolled or significant cardiovascular disease, including:
 - QTcF interval >450 msec (average of triplicate determinations)
 - Subject has bradycardia of less than 50 BPM (as determined by central reading) unless the subject has a pacemaker
 - Diagnosed or suspected long QT syndrome, or known family history of long QT syndrome
 - History of clinically relevant ventricular arrhythmias, such as ventricular tachycardia, ventricular fibrillation, or torsade de pointes
 - History of second or third degree heart block. Candidates with a history of heart block may be eligible if they currently have pacemakers, and have no history of fainting or clinically relevant arrhythmia with pacemakers.
 - Myocardial infarction within 6 months prior to screening

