5.4.4. Eligibility to Cross-Over to Quizartinib from Salvage Chemotherapy

5.4.4.1. Inclusion Criteria for Cross-Over

To be able to cross-over to quizartinib therapy from salvage chemotherapy, candidates must meet the following criteria at screening or other specified time point:

1. Provision of written informed consent approved by the IRB or IEC with privacy language in accordance with national regulations (eg, HIPAA authorization for US sites) prior to any study-related procedures, including withdrawal of prohibited medications if applicable.
2. ECOG performance score 0-2.
3. Serum creatinine $\leq 1.5 \times \text{ULN}$, or glomerular filtration rate $> 25 \text{ mL/min}$, as calculated with the Cockcroft-Gault formula.
4. Serum potassium, magnesium, and calcium (serum calcium corrected for hypoalbuminemia) within institutional normal limits. Subjects with electrolytes outside

the normal range will be eligible if these values are corrected upon retesting following any necessary supplementation.

5. Total serum bilirubin $\leq 1.5 \times \text{ULN}$.
6. Serum AST and/or ALT $\leq 2.5 \times \text{ULN}$.

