5.4.4.2. Exclusion Criteria for Cross-Over

Candidates will be excluded from cross-over to quizartinib if any of the following criteria are met at Screening or other specified time point:

1. QTcF interval > 450 msec (average of triplicate determinations.)
2. Subject has bradycardia of less than 50 BPM (as determined by central reading).
3. Uncontrolled hypertension.
4. Active infection not well controlled by antibacterial, antifungal, and/or antiviral therapy.
5. In a man whose sexual partner is a woman of childbearing potential, unwillingness or inability of the man or woman to continue to use a highly effective contraceptive method for the entire study treatment period and for at least 3 months after study treatment completion:
 - Male subjects must not freeze or donate sperm starting at Screening and throughout the study period, and 105 days after the final study drug administration.
6. In a heterosexually active woman of childbearing potential, unwillingness or inability to continue to use a highly effective contraceptive method for the entire study treatment period and for at least 3 months after study treatment completion.
 - Women are not regarded as of childbearing potential if they are post-menopausal (at least 2 years without menses) or are surgically sterile (at least 1 month before study).
 - Highly effective contraception methods include: hormonal methods associated with inhibition of ovulation, intra-uterine device; surgical sterilization (including partner's vasectomy); or sexual abstinence if this is the preferred and usual lifestyle of the subject.
 - Female subjects must not donate or retrieve, for their own use, ova from the time of screening and throughout the study treatment period, and for 12 weeks after study treatment completion.
7. Pregnancy
8. Female subjects must agree not to breastfeed from the time of Screening and throughout the study period, and for 25 days after the final study drug administration.
9. For subjects in the UK only: Refusal of permission to allow the subject's General Practitioner to be notified of his or her participation in the study.

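### The post-HSCT restart rule sets no QTcF limit and does not make normal electrolytes a condition of the first dose, unlike entry and cross-over

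*Combined protocol and SAP*

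**What the plan says.** **Restart after HSCT.** Section 5.6.4.5 gives a time window and a list of conditions: "A window of +7 days will be allowed after day 100. Quizartinib may be restarted if". The list has two items. One is neutrophil and platelet recovery without platelet transfusion support. The other is no active acute or Grade 3 or higher GVHD and no GVHD treatment begun in the previous 21 days. The synopsis (Study Treatment) has the same two items after "treatment with quizartinib may be resumed at 30 to 100 days after the transplant. Quizartinib may be restarted if", without the +7 days. The restart dose is 30 mg, or 20 mg with a strong CYP3A4 inhibitor. The only QTcF value in 5.6.4.5 governs the later dose increase: "Subjects will dose escalate starting on Day 16 if the QTcF interval is less or equal to 450 msec".

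**Entry.** Section 5.4.2 excludes "QTcF interval >450 msec (average of triplicate determinations". Section 5.4.1 requires potassium, magnesium and corrected calcium to be normal and adds: "Subjects with electrolytes outside the normal range will be eligible if these values are corrected upon retesting following any necessary supplementation".

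**Cross-over.** Section 5.4.4.2 again excludes "QTcF interval > 450 msec (average of triplicate determinations", and 5.4.4.1 repeats the electrolyte item, which begins "Serum potassium, magnesium, and calcium (serum calcium corrected for".

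**On treatment.** Section 5.6.4.4 starts dose changes at "Grade 2 (QTcF average of triplicate readings > 480 msec".

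**The concern.** Section 8.5 says that quizartinib prolongs the QT interval. Wherever a subject starts the drug for the first time, the protocol sets a QTcF ceiling and an electrolyte requirement. Cross-over is a telling comparison: its eligibility list is much shorter than the entry list, yet both limits were kept. At the post-HSCT start neither is a condition, although the same section sets 450 msec for the increase about two weeks later.

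The setting also carries QT risks that the protocol anticipates. Section 5.6.4.5 allows for strong CYP3A4 inhibitors at restart and does not bar GVHD prophylaxis. Appendix 1 lists tacrolimus and the azole antifungals as potentially QT-prolonging, and 5.6.6.1 permits such drugs when essential to care.

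What is at stake is subject safety and consistency between sites: two sites could treat the same pre-dose QTcF of, say, 465 msec differently and both comply with the restart rule.

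**Working it through.** The plan gives no figure to reproduce, so the main check is textual.

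| Decision | QTcF condition | Electrolyte condition | Section |
|---|---|---|---|
| Entry | not above 450 msec | K, Mg, corrected Ca normal; correction and retest allowed | 5.4.1, 5.4.2 |
| Cross-over | not above 450 msec | same | 5.4.4.1, 5.4.4.2 |
| Day 16 increase, including after HSCT | 450 msec or less | none listed | 5.6.4.3, 5.6.4.5 |
| Resumption after a QTcF interruption (up to 14 days) | 450 msec or less, or within 30 msec of baseline | none listed | 5.6.4.4 |
| Restart after HSCT | none | none | 5.6.4.5, synopsis |

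**Could another provision supply the missing condition?**

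- *Table 4, footnote a:* five Day 1 items (examination, vital signs, ECOG, concomitant medications, laboratory tests) are reviewed before dosing. No acceptance value is given.
- *Table 4, footnote b, and 6.2.3.1:* a triplicate ECG is taken before the Day 1 dose. The ECG row does not carry footnote a, and footnote b names no Day 1 decision. For Day 15 it does name one, as does 6.2.3.3.
- *Section 8.4:* a qualified physician at the site reviews ECGs. The example that triggers an expedited central reading is a QTcF above 480 msec.
- *Section 8.5:* electrolytes are to be kept normal, with potassium preferably over 4.0 mEq/L. This is a real target, but it is not written as a restart condition.
- *Section 5.4.5:* treatment must be withdrawn if the investigator judges that an abnormal laboratory result or clinical event makes dosing contrary to the subject's interest. The action is mandatory; the threshold is a judgement.
- *Section 5.6.4.4:* a numeric bar exists, but only after a QTcF interruption. With a baseline of 420 msec or less (420 + 30 = 450) it bars the whole 451–480 msec range. With a baseline of 445 msec it allows up to 475 msec.

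So for a subject without a QTcF interruption, nothing makes a QTcF value a bar to restart.

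**Is restart a new start or a continuation?** Quizartinib stops 7 days before conditioning and resumes no sooner than 30 days after transplant (5.6.4.5). The effective half-life of quizartinib and AC886 is about 3 days (3.3).

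- Minimum time off drug: 7 + 30 = 37 days, plus conditioning, whose length is not given.
- Half-lives: 37 / 3 = 12.3.
- Fraction remaining: 2^(−12.3) ≈ 0.0002, about 0.02%.

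The pre-dose QTcF is therefore an off-drug value, as at entry.

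**How many could be affected?** Section 5.2.5 expects about 35% of subjects to be bridged to HSCT, and 242 are planned for the quizartinib arm: 0.35 × 242 = 84.7, about 85. This assumes that the rate holds in that arm and counts every bridged subject. The share who restart, and the share of those with a QTcF above 450 msec or abnormal electrolytes, are not given, so the affected number lies anywhere from 0 to about 85.

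**Time to correct and retest.** The latest restart is Day 100 + 7 = Day 107. A subject who fails on Day 30 has 107 − 30 = 77 days. One first assessed on Day 107 has none.

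**The case against.** The strongest defence is that the comparators differ. Entry excludes prior quizartinib (5.4.2), and cross-over is for subjects who did not receive it (5.1), so both guard a first exposure. A post-HSCT subject has already taken the drug under serial triplicate ECGs. The protocol's other re-exposure rule, in 5.6.4.4, tolerates baseline + 30 msec even after Grade 3 prolongation. A flat 450 msec limit would then bar a subject at 452 msec with no QT history, while one with a baseline of 445 msec could resume at 475 msec after a Grade 3 event. Restart is also at the lowest doses; at those doses a Day 15 QTcF of 451–480 msec only blocks the increase. The Day 1 ECG before the first-ever dose carries no numeric hold either. Finally, a stable QTcF above 450 msec is not corrected by waiting, so the limit could cost a subject maintenance meant to reduce a high relapse risk (5.2.5).

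Part of this stands. Prior tolerance is relevant, the tension with 5.6.4.4 is real and must be resolved in the text, and the possible loss of maintenance is a genuine cost. It does not close the gap. The 5.6.4.4 rule covers resumption within 14 days of a QTcF interruption, not a start after at least 37 days off drug with conditioning and transplant in between. The first-ever Day 1 ECG needs no hold of its own because screening applied 450 msec within the 14 days before randomization; restart has no such screen.

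A reader might infer that post-HSCT QT monitoring is missing, or that electrolytes have no target. The documents do not support either: ECGs are scheduled before dosing, at 2 and 4 hours, and on Days 8 and 15; laboratory results and concomitant medications are reviewed before dosing; and 8.5 gives the electrolyte target.

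**Conclusion.** The point holds as a gap in the restart conditions. The lists in 5.6.4.5 and the synopsis set no QTcF limit and do not make normal electrolytes a condition of the first post-HSCT dose. Followed as written, they allow an essentially off-drug subject to start at a QTcF that would bar starting at entry or cross-over. The QTcF half is the stronger one. For electrolytes a target and a pre-dose review exist, and what is missing is the link that makes the target a condition.

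Three further inferences should be resisted.

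- Screening is not the last written check at 451–480 msec for everyone: 5.6.4.4 can bar that range later for subjects interrupted for QTcF.
- The figure of 85 is not a count of subjects at risk; it is all bridged subjects at the expected rate.
- The documents do not show that restart at 451–480 msec causes harm. The post-HSCT study described in 5.2.5 has 13 subjects at 40 or 60 mg, with both doses called well tolerated. Four stopped for SAEs of unstated type, and that section reports no QTcF result.

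The conclusion rests on the stated half-life of about 3 days and on reading the restart list as the operative rule. It concerns safety and consistency across sites and is worth an amendment. Sample size, power, alpha and the primary endpoint are unaffected.

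**What to change.** Amend the restart conditions in 5.6.4.5 and the synopsis to add:

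1. average triplicate pre-dose QTcF of 450 msec or less, which is the protocol's own starting limit;
2. potassium, magnesium and albumin-corrected calcium within institutional normal limits, with supplementation and retest allowed inside the Day 30–100 (+7) window.

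State in Table 4 footnote b and in 6.2.3.1 that the Day 1 pre-dose ECG is reviewed before the first post-HSCT dose. State in 5.6.4.4 or 5.6.4.5 that the baseline + 30 msec allowance applies only to resumption after a QTcF interruption, not to post-HSCT restart, so that it is clear which rule governs.

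No new assessment is needed: the pre-dose triplicate ECG is already scheduled, and the chemistry panel in Table 8 already includes potassium, magnesium, calcium and albumin. The drafting cost is a short amendment. The clinical cost is that some restarts will be delayed, a subject first assessed at the end of the window has no time for retest, and a subject whose QTcF stays above 450 msec would lose post-HSCT maintenance. The amendment should name that last consequence so that it is accepted knowingly.

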5.6.4.3. Quizartinib Dose Escalation Rules and Definitions

CYCLE 1 DAY 16

For subjects not taking a strong CYP3A4 inhibitor the dose of quizartinib will be increased to 60 mg/day starting on Day 16 if the subject's average QTcF (QT interval corrected with Fridericia's formula), based on triplicate reading, is ≤ 450 msec on and before Day 15.

For subjects taking a strong CYP3A4 inhibitor, the dose of quizartinib will be increased to 30 mg/day providing they meet the above QTcF requirements.

CYCLE 2 DAY 1

Subjects who fail to achieve a CR, CRp or CRi as defined in Section 7.2 after at least one 28-day cycle of therapy, and may undergo dose escalation providing the following criteria are met:

- The subject has not had a Grade 3 or higher, non-hematologic, and related adverse event.
- No increase in QTcF more than 60 msec above baseline.

- The subject must not have aplastic bone marrow at the time of the proposed dose escalation.

In addition, subjects who achieved a response (CR, CRi, CRp, or PR) at any time and who subsequently relapsed may undergo dose escalation provided they meet the same criteria as above.

For subjects not taking a strong CYP3A4 inhibitor the dose of quizartinib will be increased to 60 mg/day.

For subjects taking a strong CYP3A4 inhibitor, the dose of quizartinib will be increased to 30 mg/day providing they meet the above requirements.

Following dose escalation, triplicate ECG determinations should be performed at least once weekly for 2 weeks to monitor QTcF prolongation.

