^b Triplicate ECGs to be obtained on Day 1 of Cycle 1 post-HSCT before dosing, 2, and 4 hours after dosing; on Day 8 of Cycle 1 post-HSCT; Day 15 of Cycle 1 before dosing (including a determination of whether dose escalation is appropriate); Day 1 of Cycle 2 post-HSCT and all subsequent cycles. Following dose escalation, triplicate ECG determinations should be performed at least once weekly for 2 weeks to monitor QTcF prolongation.

^c Women of childbearing potential must have a negative urine pregnancy test before the start of study treatment and every 3 months during the treatment phase.

^d Bone marrow aspiration and biopsy for morphology determination are preferred, but biopsy may be omitted if the aspirate is considered to be adequate. Bone marrow samples are required on Day 1 of Cycle 1 post-HSCT (may be taken within 14 days prior to the first dose of study drug; this window may be extended after consultation with the Medical Monitor), on Day 1 of Cycle 4 and every 3 cycles subsequently, at the early termination/end of study visit, and as clinically indicated.

^e A bone marrow sample should be obtained at Day 1 Cycle 1 (may be taken with 14 days prior to dosing) for central determination of FLT3 mutations and mutations in other genes. FLT3 test result is not required to start quizartinib following transplantation.

^f Quizartinib should be taken in the morning.

Table 5 Schedule of Activities and Assessments for Subjects Receiving Salvage Chemotherapy

Activity	Screening (≤14 days from random- ization)	Cycle 1				Cycle 2	
		D 1	D 2 and D 8 ±1	D 15 ±3	D 29 ±14	D 1 ±3	D 15 ±3
Written informed consent	X						
Medical and disease history and demographics	X						
Physical examination	X	X	X	X		X	X
Vital sign determinations	X	X	X	X		X	X
ECOG performance status determination	X	X		X		X	X
Assessment of prior and concomitant medications	X ^a	X	X	X		X	X
Pregnancy test for women of childbearing potential	X ^b	X ^b					
Determination of coagulation profile (PT/INR)	X						
Chest X-rays (posterior/anterior and lateral)	X						
12-lead ECG (triplicate)	X ^c	X ^c	X ^c	X ^c		X ^c	X ^c
Clinical laboratory tests (hematology; chemistry; urinalysis)	X ^d	X ^d	X ^d	X ^d		X ^d	X ^d
MUGA scan or ECHO	X ^e					X ^e	
Bone marrow aspiration or biopsy	X ^f				X ^f		
Collection of bone marrow and whole blood specimen for central laboratory FLT3 mutation determination and other AML-associated mutations	X ^g						
AE/SAE assessment		X	X	X		X	X

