8.5. Management of QT Prolongation

Quizartinib is known to be associated with prolongation of the QT interval. To reduce the risk of cardiac arrhythmias, it is important to maintain serum electrolytes (K^+ , Ca^{++} , and Mg^{++}) within normal range and ideally maintain K^+ above 4.0 mEq/L. Subjects in the quizartinib arm who experience QTcF prolongation \geq Grade 2 should be managed according to the guidelines below.

- Grade 2 (QTcF average of triplicate readings > 480 msec)
 - Electrolytes (potassium, calcium and magnesium) should be checked and supplementation given to correct any values outside the normal range
 - Concomitant medications should be reviewed to identify and, if appropriate, discontinue any medication with known QT prolonging effects
 - The dose of quizartinib will be reduced one level without interruption of dosing
 - Quizartinib dose may be re-escalated after 1 cycle at reduced dose if QT prolongation has decreased to \leq Grade 1 but subject must be monitored closely for QT prolongation for first cycle at the increased dose.
- Grade 3 (QTcF average of triplicate readings > 500 msec)
 - Electrolytes (potassium, calcium and magnesium) should be checked and supplementation given to correct any values outside the normal range
 - Concomitant medications should be reviewed to identify and, if appropriate, discontinue any medication with known QT prolonging effects
 - Quizartinib dosing will be interrupted for up to 14 days. If QTcF returns to within 30 msec of baseline or ≤ 450 msec within 14 days, treatment may be resumed at a

reduced dose. Quizartinib dose cannot be escalated following dose reduction for Grade 3 QTcF prolongation.

- Grade 4 (QTcF average of triplicate readings >500 msec or >60 msec change from baseline, and Torsade de pointes or polymorphic ventricular tachycardia or signs/symptoms of serious arrhythmia)
 - Electrolytes (potassium, calcium and magnesium) should be checked and supplementation given to correct any values outside the normal range
 - Concomitant medications should be reviewed to identify and, if appropriate, discontinue any medication with known QT prolonging effects
 - Quizartinib dosing will be permanently discontinued.

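### The post-HSCT escalation rule in 5.6.4.5 omits the bar on escalating after a Grade 3 QTcF dose reduction that 8.5 states without qualification

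*Combined protocol and SAP*

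**What the plan says.** **Restart after HSCT (5.6.4.5).** Quizartinib may be resumed 30 to 100 days after transplant. The restart criteria concern neutrophil and platelet recovery and GVHD; none concerns QTcF history. On dose: "The starting dose of quizartinib post-HSCT should be 30 mg daily unless the subject is receiving a strong CYP3A4 inhibitor", in which case it is 20 mg. Then: "Subjects will dose escalate starting on Day 16 if the QTcF interval is less or equal to 450 msec", read before or at the Day 15 ECG. The section does not refer to 8.5.

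**Grade 3 QTcF prolongation (8.5).** After interruption and recovery, treatment may resume at a reduced dose, and then: "Quizartinib dose cannot be escalated following dose reduction for Grade 3 QTcF prolongation".

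**Supporting text.** Section 5.6.4.4 says subjects on a reduced dose "may be re-escalated one level to 30 mg/day or to 60 mg/day except for reductions due to Grade 3 QTcF prolongation". The synopsis says "the dose may be re-escalated stepwise from 20 mg to 30 mg to 60 mg, except following Grade 3 QTcF prolongation".

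**First-time escalation (5.6.4.3).** The Cycle 1 Day 16 step is taken if average QTcF, "based on triplicate reading, is ≤ 450 msec on and before Day 15".

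**Post-HSCT visit schedule.** Table 4, footnote b, calls for an ECG on "Day 15 of Cycle 1 before dosing (including a determination of whether dose escalation is appropriate"; 6.2.3.3 carries the same parenthesis.

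**The concern.** Grade 3 QTcF prolongation does not end treatment. A subject can recover, resume at a lower dose, respond, and go to transplant with that reduction on record. At restart, a site that follows 5.6.4.5 as written would escalate on Day 16. A site that follows 8.5 would not.

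What is at stake is returning a subject to the dose at which QTcF exceeded 500 msec, on a drug whose QT effect the protocol describes as clearly dose dependent (5.2.3). It also leaves sites unsure which action complies, because 14.7 lists an incorrect study drug dose as an example of a protocol deviation. This is a matter of dosing safety and consistency. The survival analysis is not involved.

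**Working it through.** The plan states no figure on this point to reproduce. The check is a comparison of rules, followed by a rough count.

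**1. One subject under both rules.** Take a subject with Grade 3 prolongation at 60 mg/day, reduced to 30 mg/day, then transplanted, and not on a strong CYP3A4 inhibitor.

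| Step | 5.6.4.5 | 8.5 |
|---|---|---|
| Restart | 30 mg/day | No restart dose stated |
| Day 16, QTcF ≤ 450 msec | Escalate | Escalation barred |

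5.6.4.5 does not name the Day 16 target, but 60 mg is the only level above 30 mg in the dosing rules. The instructions are opposite for this subject.

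**2. Does the 450 msec condition replace the bar?** Not reliably. It is read at the restart dose, not at the dose that caused the event. It is also essentially the Cycle 1 Day 16 condition in 5.6.4.3. A subject who first reached 60 mg by that step had already met it before the Grade 3 event. For a subject who reached 60 mg by the Cycle 2 Day 1 route, which has no 450 msec criterion, it may screen out more.

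**3. Does the protocol use history elsewhere?** Yes. The Cycle 2 Day 1 rule in 5.6.4.3 excludes subjects who have had a related non-hematologic event of Grade 3 or higher, and the re-escalation rules exclude Grade 3 QTcF. The post-HSCT rule has no such criterion.

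**4. Subjects limited to 20 mg/day.** Someone held at 20 mg after Grade 3 prolongation, and not on a strong inhibitor, would restart at 30 mg under 5.6.4.5, above the earlier limit from the first day. This conflict is softer: the restart dose is worded as a recommendation, and 8.5 bars escalation without capping a restart. For a subject already at 20 mg when the event occurs, 5.6.4.4 says "If 20 mg/day is the current dose, dosing will be interrupted for up to 14 days" and allows resumption at 20 mg. No reduction takes place, so the wording of 8.5 does not literally reach that subject.

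Inhibitor status matters here. Section 5.2.4 reports about a 2-fold rise in exposure with a strong inhibitor. If exposure is proportional to dose, 20 mg with an inhibitor resembles 20 × 2 = 40 mg without one. Holding such a subject at 20 mg after the inhibitor is withdrawn would give about 20/40 = half the exposure previously allowed.

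**5. How many subjects.**

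- Bridged to HSCT: 242 × 0.35 = 84.7 (35% is the protocol's projection in 5.2.5).
- Grade 3 rate: Table 2 gives 5% of 38 at 30 mg and 3% of 36 at 60 mg, that is 2/38 and 1/36. Adding the Grade 2 counts of 2 and 5 gives 4/38 and 6/36, which match 5.2.3. Pooled: 3/74 = 4.05%, exact (Clopper-Pearson) 95% interval 0.84% to 11.39%.

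| Assumption | Expected number | Range from the interval |
|---|---|---|
| All bridged restart, all Grade 3 resume | 84.7 × 3/74 = 3.4 | 0.7 to 9.7 |
| One of these fractions is 50% | 1.7 | 0.4 to 4.8 |
| Both are 50% | 0.9 | 0.2 to 2.4 |

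The documents give neither fraction; 50% is illustrative. No row is discounted for subjects who fail the 450 msec condition.

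**The case against.** The strongest reply is that the two rules can be obeyed together: 8.5 is a specific prohibition, 5.6.4.5 a general schedule, and a site that withholds escalation is treating the first as an exception to the second. The bar also appears in 5.6.4.4, in the paragraph just before 5.6.4.5, and in the synopsis just before its HSCT paragraph. The Day 15 visit asks whether escalation is appropriate, which leaves room to apply 8.5. Post-HSCT ECGs are taken on Days 1, 8 and 15 and at least weekly for two weeks after escalation, and the reduction and interruption rules still apply.

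Much of this stands. It shows what the sponsor most likely intends and it bounds the risk. It does not remove the conflict. No text ranks 8.5 above 5.6.4.5. The passages in 5.6.4.4 and the synopsis are worded for subjects currently on a reduced dose. The Day 15 determination names no criterion based on QTcF history. The pointer to 8.5 in the treatment overview (5.1.2) concerns prolongation when it is observed. Monitoring detects a recurrence but does not prevent the re-exposure.

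Three stronger readings are tempting, and the documents do not support them:

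- *The bar is meant to lapse after transplant.* Nothing says so; 5.6.4.5 is silent.
- *Every subject with a Grade 3 reduction must restart no higher than the reduced dose.* Section 8.5 sets no restart cap, and a blanket cap would ignore whether the event occurred on a strong inhibitor since withdrawn.
- *About three subjects will be re-exposed.* That is the expected number if all restart and all resume, before the 450 msec condition is applied.

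**Conclusion.** The conflict is real and the rule in 5.6.4.5 should be corrected. Followed as written, it can send a subject back to the dose that produced Grade 3 QTcF prolongation, which 8.5 forbids.

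The size is small: about 3 subjects expected if all bridged subjects restart and all Grade 3 subjects resume, about 1 to 2 if half do, and fewer once the 450 msec condition is applied. The estimate assumes that transplanted subjects share the Phase 2b Grade 3 rate. That rate rests on 3 events and is classified by starting dose: 63% of the 30 mg group later went to 60 mg, and 19% of the 60 mg group went to 90 mg, a dose not used here. The 35% bridging figure matches that of Phase 2 Cohort 2, in a study dosed at 90 to 200 mg. The finding rests on the text and would stand with a different count. The restart dose for subjects limited to 20 mg is a secondary point.

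**What to change.** Add to 5.6.4.5: *Subjects whose dose was reduced for Grade 3 QTcF prolongation before HSCT do not escalate on Day 16 (see Section 8.5).*

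As a secondary change, state there that a subject limited to 20 mg/day after Grade 3 QTcF prolongation while not on a strong CYP3A4 inhibitor restarts at 20 mg/day. This should not apply automatically to a subject whose event occurred on a strong inhibitor since withdrawn. If the sponsor does intend the bar to lapse after transplant, 5.6.4.5 and 8.5 should both say so.

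No new visit or procedure is needed. Slightly fewer subjects would escalate after HSCT. As a dosing change it goes through a routine amendment, with the prior IRB/IEC approval that 14.3 requires, at approximately 150 centers.
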